7.2 Data Analysis

Appropriate statistical tools will be used to test for significance with respect to the primary and secondary endpoints.

Categorical variables will be reported as a percentage and continuous variables as mean \pm standard deviation (SD) or median and interquartile range (IQR), as appropriate. Differences in categorical variables will be assessed using the Chi squared test or the Fischer's Exact test and for the analysis of continuous variables the Student's t test or the Mann-Whitney U test will be used, where appropriate. P values <0.05 are considered significant. Patients that die during the trial duration will also be included in the statistical analysis.

The primary endpoint analysis will consist of a one-sided fisher-exact test in which the proportion of cases of IAA will be compared between both groups. The population included in this analysis will consist of a modified intent to treat population. This MITT population consists of all patients that received at least 1 posaco/placebo administration but excluding the patients in which a diagnosis of IAA was made on the basis of the BAL sample taken on day 1 because these patients in fact had an IAA at the day of inclusion.

8 Data handling

Patient data will be encoded: which means that personal data can only be related to an identified or identifiable person by means of a code.

Demographic, biochemical, microbiological and radiological data will be collected prospectively as a part of clinical routine. Samples will be obtained for characterization of the influenza type and for *Aspergillus* diagnosis including culture, galactomannan and PCR. These samples are part of daily routine, no additional samples for this study will be taken. All *Aspergillus* colonies will be screened for azole resistance, using an agar-based selection tool, and relevant samples, i.e. BAL fluid, will be stored for direct detection of resistance mutations by PCR. Clinical *A. fumigatus* isolates will be sent the National Mycology Reference Laboratory in Leuven (Belgium) or Nijmegen (the Netherlands) for MIC-testing and analysis of azole-resistance mutations. A blinded data review committee following a pre-defined case definition will classify patients with evidence for primary and breakthrough IAA-infection.

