Prinicpal Investigators and Participating Sites	[name]. [name], Intensivist, UZ Leuven [name]. [name], Medical microbiologist, UMC Radboud Nijmegen
Medical condition or disease under investigation	Influenza-associated pulmonary aspergillosis (IAA)
Purpose of clinical trial	Study the effect of antifungal prophylaxis on the incidence of IAA in critically ill patients with severe influenza.
Primary objective	Study if antifungal prophylaxis can decrease the incidence of IAA compared to SOC in critically ill patients with severe influenza pneumonia.
Secondary objective(s)	
Trial Design	Interventional non-blinded randomized controlled multicenter study
Endpoints	The IAA incidence at ICU discharge is the primary endpoint and will be compared in patients receiving posaconazole prophylaxis with those receiving SOC. Secondary outcomes will be time to IAA diagnosis, length of ICU stay, length of hospital stay, 30-day mortality and 90-day mortality
Sample Size	50 patients in each arm
IMP, dosage and route of administration	Posaconazole, 2*300mg/d on day 1, followed by 1*300mg/d from day 2 until day 7, intravenously administrated
Active product(s)	comparator None, SOC
Maximum duration of treatment of a Subject	7 days of prophylaxis

Maximum duration of Trial	4 influenza seasons (the first two influenza seasons will be supported by MSD)
Anticipate First Patient First Visit (FPFV)	Expected 01/12/2017
Anticipate Last Patient Last Visit (LPLV)	Expected 30/03/2021

TRIAL FLOWCHART

Schedule of Events – Trial specific Procedures / Assessments

EVENTS	Screening	Randomization	Treatment Period	ICU discharge	Follow-Up Visits (phone call)
Timing (weeks)		Day 1	Day 2 - ICU discharge		Day 30 and day 90
Informed consent ^a	X				
PCR-confirmed influenza ^b	X				
Inclusion/Exclusion	X	X			
Demographics; Medical history	X				
Symptom directed physical examination	X	X	X	X	
Weight / Height	X				
Vital Signs	X	X	X	X	
Randomization		X			
Microbiology sampling	X	X ^c	X ^d	X	
Chemistry : laboratory measurements	X	X	X	X	
Radiological Assessments (CT / RX)		X	X		
Trial drug administration (max 7 days)		X	X		
IAA mycological evidence ^e	X	X	X	X	X
IAA signs and symptoms assessment	X	X	X	X	
Survival status		X	X	X	X
Adverse event (AE) assessment ^f			→		
Serious Adverse Event (SAE) assessment				→	
Concomitant Medication (CM)					

a: Informed Consent process should take place prior to all other trial-related procedures at the screening visit

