2.3 Secondary Endpoints

[figure not shown]
Secondary outcomes will be time to IAA diagnosis, length of ICU stay, length of hospital stay, **30-day mortality** and 90-day mortality.

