4.1 Inclusion criteria

Patients eligible for inclusion in this trial have to meet **all** of the following criteria:

1. Written informed consent must be obtained from the patient or his/her legal representative prior to any study procedures
2. Adult patient (≥ 18 years)
3. PCR-confirmed influenza based on nasopharyngeal swab (NS), bronchial aspirate (BA) or broncho-alveolar lavage (BAL) within 7 days before ICU admission or within 48 hours after ICU admission.
If PCR is not available a positive result of a rapid test is required (a negative rapid test does not imply absence of influenza and thus requires confirmation by PCR)
4. Influenza symptoms present for no more than 10 days before ICU admission
5. Respiratory distress as the main reason for ICU admission. Respiratory distress will be defined as tachypnea with an respiratory rate ≥ 25 x/min and a $\text{paO}_2/\text{FiO}_2$ -ratio ≤ 300 with or without (bilateral) infiltrates.

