5.5 Visit schedule and assessments

5.5.1 Screening/ Baseline

After eligibility screening and signing the trial ICF, the following screening assessments will be done:

- Patient demographics and baseline parameters (SOC)
- Medical History (SOC)

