8.1 Data Collection Tools and Source Document Identification

Source data will be collected and recorded in the trial participants files/medical records. They will be kept on a secured location at all times. The collection and processing of source data (from subjects enrolled in this trial) will be limited to those data that are necessary to fulfill the objectives of the trial. These data

must be collected and processed with adequate precautions to ensure confidentiality and compliance with applicable data privacy protection laws and regulations. Appropriate technical and organizational measures to protect the data against unauthorized disclosures or access, accidental or unlawful destruction, or accidental loss or alteration must be put in place. Personnel whose responsibilities require access to personal data agree to keep the data confidential.

Documentation of source data is necessary for the evaluation and validation of clinical findings, observations and other activities during a clinical trial. Source documentation serves to substantiate the integrity of trial data, confirms observations that are recorded and confirms the existence of trial participants. Furthermore source documentation must be available for the following to confirm data collected in the (e)CRF: subject identification, eligibility, and trial identification; trial discussion and date of informed consent; dates of visits; results of safety and efficacy parameters as required by the protocol; record of all adverse events and follow-up of adverse events; concomitant medication; drug receipt/dispensing/return records; trial drug administration information; and date of trial completion and reason for early discontinuation of trial drug or withdrawal from the trial, if applicable.

Data collection is the responsibility of the clinical trial staff at the site under the supervision of the investigator. The investigator will maintain complete and accurate documentation for the trial. All source documents will be reviewed by the clinical team to ensure that they are accurate and complete.

As defined in section 1.52 of the ICH Guideline for Good Clinical Practice (latest version of ICH E6) source documents may include: original documents, data and records (e.g. hospital records, clinical and office charts, laboratory notes....)

Case report forms

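### Section 7.2 compares 30-day and 90-day mortality without baseline adjustment; pre-specifying age and the eligibility paO2/FiO2 ratio as covariates would be a cheap, modest gain, not the repair of an error

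*Combined protocol and SAP*

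**What the plan says.** The synopsis lists the secondary endpoints: "Secondary outcomes will be time to IAA diagnosis, length of ICU stay, length of hospital stay, 30-day mortality and 90-day mortality". Section 2.3 repeats the list. Section 7.2 has no separate paragraph on mortality, so the general rule for categorical data applies: "Differences in categorical variables will be assessed using the Chi squared test or the Fischer's Exact test". The only other guidance is broad: "Appropriate statistical tools will be used to test for significance with respect to the primary and secondary endpoints". No section names a covariate, a regression model or a stratified test for an efficacy endpoint. The only covariate analysis is in the pharmacokinetic substudy (PK section 3.3).

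Section 5.4 provides for block randomisation and names no stratification factor.

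On baseline data, section 5.5.1 and the flowchart collect demographics at screening. Inclusion criterion 5 in section 4.1 requires a respiratory rate of at least 25 per minute and a paO2/FiO2 "ratio ≤ 300 with or without (bilateral) infiltrates". Section 8.1 adds that "source documentation must be available for the following to confirm data collected in the (e)CRF: subject identification, eligibility, and trial identification".

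**The concern.** Mortality is the outcome that matters most to patients, and with about 100 patients it rests on few deaths. Age and oxygenation can be expected to predict death in critically ill patients. With no stratification and no adjustment, a chance difference between the arms in these variables feeds straight into the observed mortality difference. The unadjusted standard error allows for this on average over repeated trials, but the single estimate that the trial reports is not corrected for it.

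If an imbalance appears and the team adjusts only then, the analysis is post hoc and open to challenge, the more so in an open-label trial. The choice is therefore best fixed before the data are seen.

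**Working it through.** **1. The plan's own figure.** Section 7.1 gives 47 per arm for IAA at 25% v 5%, 80% power, one-sided. Taking alpha as 0.05 from section 7.2:

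- Uncorrected: n = [1.645·√(2·0.15·0.85) + 0.842·√(0.25·0.75 + 0.05·0.95)]² / 0.20² = 38.4, so 39.
- Continuity-corrected: (38.4/4)·[1 + √(1 + 4/(38.4·0.20))]² = 47.8, so 48.

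The 47 is reproduced to within one patient. A two-sided unpooled formula also gives 47, so the text does not settle which was used; nothing here depends on it. The plan gives no corresponding figure for mortality.

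**2. Inputs for mortality.** I take 50 per arm, from the target of at least 100 in the MITT population (section 7.1). Mortality and covariate strength are assumptions, shown as ranges.

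**3. Precision.** The unadjusted half-width of the 95% CI is 1.96·√(2p(1−p)/50). If adjustment cuts the variance by a fraction v, it is multiplied by √(1−v).

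| Mortality p | Unadjusted | v = 5% | v = 10% | v = 20% |
|---|---|---|---|---|
| 20% | 15.7 points | 15.3 | 14.9 | 14.0 |
| 30% | 18.0 points | 17.5 | 17.0 | 16.1 |
| 40% | 19.2 points | 18.7 | 18.2 | 17.2 |

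The factor √(1−v) makes the interval 2.5%, 5% and 11% narrower. An adjusted trial of 100 is worth 100/(1−v) = 105, 111 or 125 patients.

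**4. Plausible v.** Two approaches, both on assumed strengths:

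- With odds ratios per SD for age and oxygenation of 1.3/1.2, 1.5/1.3 and 2.0/1.5, at 20% to 30% mortality, the variance explained is about 2%, 4% and 9% to 11%. The interval is then about 1% to 6% narrower.
- Simulation of 4000 trials per scenario used two standard normal covariates, logit slopes of 0.55, 1.0 and 1.35 on their scaled sum (AUC 0.65, 0.74, 0.80), and mortality of 30% v 15%. The SD of the risk difference fell from 0.0814 to 0.0799, from 0.0834 to 0.0785 and from 0.0817 to 0.0740. As 1 − (adjusted/unadjusted)², these are variance cuts of 4%, 11% and 18%. Repeat runs gave 2% to 3%, 10% to 11% and 20% to 22%. Both estimates were unbiased.

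**5. A mortality difference consistent with the plan.** Section 7.1 plans IAA at 25% v 5%, and section 1 reports 61% mortality in IAA. If prophylaxis affects death only by preventing IAA, and mortality without IAA is m (assumed), the difference is 0.20·(0.61 − m). Its ceiling, at m = 0, is 12.2 points. With m = 20%:

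- SOC: 0.25·0.61 + 0.75·0.20 = 30.25%
- Posaconazole: 0.05·0.61 + 0.95·0.20 = 22.05%
- Difference: 8.2 points, that is about 30% v 22%.

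**6. Power at that difference.** The standard error is √(0.3025·0.6975/50 + 0.2205·0.7795/50) = 0.0875, and 0.082/0.0875 = 0.937. Two-sided power at 5% is Φ(0.937 − 1.96) + Φ(−0.937 − 1.96) = 15.5%. Dividing 0.937 by √(1−v) for v = 4%, 11% and 18% gives 16.0%, 16.8% and 17.9%. The same calculation gives 27.1%, rising to 28.1%, 29.9% and 32.0%, for m = 10%; and 10.0%, rising to 10.2%, 10.6% and 11.1%, for m = 30%. At 30% v 22%, simulated tests, which do not have exactly equal size, show gains of about 1 to 4 points.

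**7. Chance imbalance.** For a standardised prognostic score, the arm difference has SD √(2/50) = 0.20, so it exceeds 0.3 SD in either direction with probability P(|Z| > 1.5) = 13%. In simulated trials where the posaconazole arm was sicker by more than that, the unadjusted mortality difference moved on average by 3.7, 6.0 or 7.0 points across the three strengths. The adjusted estimate moved by less than half a point.

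**8. Cost in test size.** Under no effect, the adjusted test with an uncorrected standard error rejected in 5.3% to about 7% of simulated trials, depending on the run, against 4.5% to about 6% unadjusted.

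**The case against.** The strongest reply is that nothing here is wrong. Unadjusted chi-squared and Fisher tests are valid in a randomised trial, mortality is secondary with no stated power, and the trial is a proof of concept on IAA incidence. All of that stands, and it is why this is an improvement to consider and not an error.

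Three stronger readings are tempting and are not supported:

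- **That adjustment would raise power materially.** At 30% v 15%, simulated power rises from about 44% to 53% with strong covariates. But a 15-point difference exceeds the 12-point ceiling implied by the plan's own IAA figures if prophylaxis acts only through IAA. Part of the rise is also test size: at 44% power, moving the size from 5.0% to 5.3% adds about 1 point by itself.
- **That the covariates are known to be strong.** No figure in the documents says so. Criterion 5 truncates both paO2/FiO2 and respiratory rate, which tends to weaken prediction within the trial.
- **That baseline oxygenation is in the database for every patient.** Criterion 5 means it must be known, but no section lists the value as an (e)CRF field, and an eligibility tick could satisfy section 8.1. The value also relates to ICU admission and may predate randomisation, since influenza may be confirmed up to 48 hours after admission.

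On the other side, the sentence about appropriate tools does not answer the point. It would permit an adjusted analysis but fixes neither model nor covariates.

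**Conclusion.** The point holds as a cheap improvement. Section 7.2 gives up some precision on 30-day and 90-day mortality, and some protection against chance imbalance. With 50 per arm and assumed weak to strong covariates, the variance reduction is about 3% to 20%, or a 95% CI roughly 1% to 11% narrower. At a mortality difference in line with the plan's IAA assumptions (about 30% v 22%), power rises by about 1 to 4 points from a base of about 15%, so the conclusion on mortality would rarely change. The better reason to act is that an adjusted estimate fixed in advance can be relied on if the arms turn out unequal in age or severity.

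These sizes rest on assumed mortality and prognostic strength, and the 30% v 22% scenario on prophylaxis acting only through IAA. A reader should not infer that the planned mortality comparison is biased or invalid.

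**What to change.** In section 7.2, before any data review:

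- Pre-specify a logistic regression of 30-day mortality, and likewise of 90-day mortality, on arm, age and the paO2/FiO2 value used for eligibility.
- Report the standardised (marginal) risk difference with a 95% CI from a small-sample-corrected standard error, alongside the unadjusted comparison.
- State how a missing covariate value will be handled.
- Confirm that the (e)CRF holds the paO2/FiO2 value and not only a yes/no tick.
- Leave the primary one-sided Fisher test unchanged. It rests on about 50·0.25 + 50·0.05 = 15 expected IAA cases, too few for adjustment to be dependable.

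Two covariates are feasible for mortality: at 20% to 40% mortality, 100 patients give about 20 to 40 deaths. The cost is a paragraph of text, a few lines of code and possibly one (e)CRF field, with no new visits or samples. The downside is a slightly liberal adjusted test at this size: about 1 point or a little more without the correction, less with it. Showing the unadjusted result beside it keeps this visible.

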2.4 Trial Design

This study is an interventional non-blinded randomized controlled multicenter study.

- Critically ill patients with PCR-confirmed influenza (for details: see inclusion criteria) are eligible for inclusion in this study and will be randomized to or the posaconazole prophylaxis group or the SOC group. Within 48 hours after influenza diagnosis with a bronchoscopy with BAL (minimum volume of 2x20mL, 0.9% NaCl) and a with a serum galactomannan will be performed as part of routine ICU care in this type of patients. As any bronchoscopy, this bronchoscopy will only be performed if the safety of the patient will not be compromised. If an IAA-infection is suspected based on the result of this BAL ((A) *Aspergillus* cultured from BAL, or (B) a galactomannan (GM) ≥ 1 in BAL or ≥ 0.5 in serum), the patient will be withdrawn from the study and antifungal treatment will be started. The type and duration of antifungal therapy will be at the discretion of the treating physician.
- SOC further includes:
 - The treating physician can decide to perform an additional bronchoscopy with BAL between day 2 after randomisation and ICU discharge in case of respiratory deterioration and clinical suspicion of an IAA-infection. Any bronchoscopy will only be performed if the safety of the patient will not be compromised. In case of positive mycological evidence of an IAA-infection, a CT thorax without IV contrast is performed if possible. If an IAA-infection is documented, antifungal treatment will be started and - in case the IAA-infection is diagnosed before the ending of the study drug - the patient will be withdrawn from the study. Again, type and duration of antifungal therapy will be at the discretion of the treating physician.

- Oseltamivir (non-IMP) will be started at the discretion of the treating physician from the first day of ICU admission as 2*150 mg/day for a duration of 10 days. If oseltamivir had already been started up before ICU admission, oseltamivir treatment will be continued up to a total of 10 days.

*If *Aspergillus* is **only** cultured from sputum (and not from BAL) within the first 48 hours after the influenza diagnosis, the patient will not be withdrawn from the study

3 Trial Medication / Drug

Drug Name	IMP or non-IMP
Posaconazole	IMP

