4.4 Withdrawal criteria

The subject may withdraw consent at will at any time. The subject's request to withdraw from the trial must always be respected. Patients will also be withdrawn from the study when an IAA-infection is diagnosed based on clinical and mycological evidence with radiological abnormalities, between day 1 and day 7 of posaconazole prophylaxis. At that time antifungal treatment will be started. The type and duration of antifungal therapy will be at the discretion of the treating physician.

5 Trial Procedures

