5.5.2 Treatment Visits

Day 1 = day of randomization:

- Bronchoscopy with BAL sampling, serum galactomannan (SOC)
- Pregnancy screening negative
- Start study medication
- Gather baseline clinical data including demographic, biochemical, microbiological and radiological data (SOC)

Day 2 – ICU discharge:

- Withdrawal of patients from study if mycological evidence of IAA-infection on BAL of day 1
- Continuation of study medication up to day 7
- Gather clinical data including demographic, biochemical, microbiological and radiological data (SOC)
- Assess presence of IAA-infection (SOC)
- Assess outcome parameters: ICU mortality, IAA-infection (SOC)

30 days after randomization:

Assess outcome parameters: hospital and/or 30-day mortality and a retrospective assessment of IAA-infection (SOC)

90 days after randomization:

- Assess outcome parameters: hospital and/or 90-day mortality and a retrospective assessment of IAA-infection (SOC)

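### Section 7.2 gives time to IAA diagnosis no time-to-event method or horizon, and gives no rule for stays ended by death; unless a rule is added, the named tests compare IAA cases only

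*Combined protocol and SAP*

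**What the plan says.** Section 2.3 lists the durations: "Secondary outcomes will be time to IAA diagnosis, length of ICU stay, length of hospital stay". With 30-day and 90-day mortality they make five secondary outcomes, three of them times.

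Section 7.2 opens with a general statement: "Appropriate statistical tools will be used to test for significance with respect to the primary and secondary endpoints". It then names chi-squared or Fisher for categorical variables and, for continuous ones, that the Student's "t test or the Mann-Whitney U test will be used, where appropriate". The primary endpoint has its own one-sided Fisher exact test in a modified intent-to-treat (MITT) population. No analysis population is named for the secondary outcomes.

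On deaths, section 7.2 says: "Patients that die during the trial duration will also be included in the statistical analysis". It does not say what value a stay or an IAA-free time takes when death ends it. No section names a censoring rule, Kaplan-Meier, log-rank, Cox, cumulative incidence or any competing-risk method.

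The horizon for time to IAA is also open. The synopsis says "The IAA incidence at ICU discharge is the primary endpoint", while section 5.5.2 also plans a retrospective IAA assessment at day 30 and again at day 90.

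**The concern.** A patient who never develops IAA has no time to diagnosis. A t test or Mann-Whitney test needs a number for every patient it uses. Without a rule that gives IAA-free patients a value (a worst rank, for example), the test can use only the cases.

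Who becomes a case is what posaconazole is meant to change. The cases in the two arms are therefore not comparable by randomisation. Their comparison asks whether the cases that occurred came earlier or later, not whether IAA was prevented or delayed. A null result could then be reported as no effect on time to IAA beside a clearly positive primary result.

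For length of stay, a raw comparison counts an early death as a short stay. If prophylaxis saves lives, this works against the posaconazole arm.

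**Working it through.** **Inputs from the documents.** Incidence 25% vs 5%, 80% power, one-sided test, 47 per arm needed, at least 100 in the MITT (50 per arm), 55 per arm enrolled (section 7.1). Significance level 0.05 (section 7.2; section 7.1 gives none). Cited cohort: 16% IAA incidence, 61% mortality in IAA (Background and Rationale).

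**The plan's own figure.** With pooled p = 0.15 and difference 0.20, n = [1.645·√(2·0.15·0.85) + 0.842·√(0.25·0.75 + 0.05·0.95)]² / 0.20² ≈ 38.4. With continuity correction, n = (38.4/4)·[1 + √(1 + 4/(38.4·0.20))]² ≈ 47.8, so 48 per arm, within one of the stated 47. Exact one-sided Fisher power is 82.7% at 47 per arm and 85.3% at 50.

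**Who has a time to IAA.**
- Expected cases at 50 per arm: 50·0.25 = 12.5 and 50·0.05 = 2.5. That is 15 patients with a time and 85 without.
- At 55 per arm: 13.75 vs 2.75.
- At 16% with the same 80% reduction (3.2%), 50 per arm: 8.0 vs 1.6.
- No posaconazole case: 0.95^50 = 7.7% of trials; at 3.2%, 0.968^50 = 19.7%.

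**What an exact case-only Mann-Whitney test can show.** With a and b cases, the smallest two-sided p is 2/C(a+b, b). For 12 vs 1 this is 2/13 = 0.154; for 12 vs 2 it is 2/91 = 0.022. Over the binomial distributions of a and b, p < 0.05 is out of reach (or an arm is empty) in 29% of trials at 25% vs 5%, and in 65% at 16% vs 3.2%. This limit does not apply to the t test.

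**How often case-only tests reject, by assumed case timing.** Simulation at 25% vs 5%, 50 per arm, two-sided 0.05, no competing events; trials with an empty arm count as not significant.

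| Assumed timing | Mann-Whitney | t test |
|---|---|---|
| Rate cut equally over time (Weibull shapes 0.5, 1, 2) | about 2–4% | about 4–5% |
| 14-day horizon, posaconazole cases only after day 7, control cases uniform | about 12–13% | about 15% |
| As above, control cases clustered early (exponential, mean 4 days) | about 48–55% | about 65–72% |

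In the first row a log-rank test in all 100 patients rejects in about 84% of trials. The reason for the low case-only rates is that mean time among cases barely differs. For constant hazard l = −ln(1−p) and horizon 1, the mean is 1/l − 1/(e^l − 1), which is 0.476 at 25% and 0.496 at 5%.

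**Precision of an all-patient analysis.** SE(log HR) ≈ √(1/12.5 + 1/2.5) = 0.693. The 95% interval is a factor of exp(1.96·0.693) = 3.9 either way. With 8 vs 1.6 events, the SE is 0.866 and the factor 5.5. When one arm has no case there is no finite hazard ratio and this interval does not apply.

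**Length of stay.** Prevented cases per 50: 12.5 − 2.5 = 10. Assumptions not in the documents: mortality 10–40% when IAA is prevented, death 5–15 days before the discharge that would have occurred, SD of stay 10–15 days. Fewer deaths: 10·(0.61 − 0.40) = 2.1 to 10·(0.61 − 0.10) = 5.1. Shift in mean raw stay: 2.1/50·5 = 0.2 to 5.1/50·15 = 1.5 days. Standard error of the mean difference: SD·√(2/50) = 2.0 to 3.0 days.

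**The case against.** **The plan prescribes no case-only test.** Section 7.2 never assigns the t test or Mann-Whitney to time to IAA, never says to drop IAA-free patients, and its opening sentence leaves room for a survival method. This stands: the defect is a missing rule, not a planned wrong test. But the sentence supplies no method, population or horizon, and in a non-blinded trial the choice should not wait until the data are seen.

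**Low rejection is one scenario.** A reader might infer that the named tests would almost always miss an 80% reduction. The documents do not support that. Nothing in them says the rate is cut equally over time; prophylaxis is short while IAA is counted to ICU discharge, so late breakthrough cases are plausible and rejection could be far higher. The selection problem remains under every timing pattern.

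**Nothing primary is lost.** The primary Fisher test has 85.3% power for the same reduction, against about 84% for the log-rank test. This stands. Setting 84% beside 2–4% compares two different questions and does not measure power lost to the trial.

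**Patients withdrawn at IAA diagnosis.** Section 4.4 says "Patients will also be withdrawn from the study when an IAA-infection is diagnosed" during prophylaxis, and section 2.4 says the same "in case the IAA-infection is diagnosed before the ending of the study drug". A reader might infer that their stay and survival data are lost. The documents do not support this. Stay lengths are declared outcomes, section 5.5.3 stops assessments only on withdrawal of consent, data after ICU discharge come from the medical file (5.5.4), and serious adverse events, including deaths, are reported to day 90 (6.3.2).

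**The stay distortion rests on assumed inputs.** It does, and even so it is smaller than the standard error.

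**Conclusion.** The point holds as a gap in specification with a concrete consequence. Unless a rule is added, the only named tests reduce time to IAA to about 12.5 vs 2.5 cases chosen by the outcome, with no comparison possible in 7.7% of trials (19.7% at 16% vs 3.2%). These figures rest on the plan's rates and on 50 per arm in the analysis. The rejection rates rest on assumed case timing and should be read as a range.

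The missing rule for stays ended by death is real, but its effect is probably small: 0.2–1.5 days against a standard error of 2–3 days, on assumed inputs.

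The change should be made, but only secondary outcomes of a proof-of-concept trial are at stake.

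**What to change.** In section 7.2:

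1. Analyse time from randomisation to IAA diagnosis in all patients of the primary analysis population, as finally defined. Use cumulative incidence curves by arm and a cause-specific log-rank test.
2. State one horizon. If it is ICU discharge, death and ICU discharge alive are competing events. If it is day 30 or day 90, death is the competing event.
3. Report a Cox hazard ratio only if both arms have cases.
4. For ICU and hospital stay, add one pre-specified death-aware summary next to the planned comparison, such as time to discharge alive with death as a competing event.

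The cost is SAP wording and a little more analysis work, with no extra patients, samples or visits. The downside is that the time-to-IAA result will largely repeat the primary incidence result and, with about 15 events, will be imprecise.
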